6.2. Baseline Assessments

6.2.1. Demography

The investigator will record demographic data, including (but not limited to) age, gender, race, and will measure height (also used for BMI calculation).

6.2.2. Medical history, concomitant diseases

In an interview, medical history will be evaluated by the investigator in order to determine whether the subject fulfils the inclusion criteria and meets none of the exclusion criteria. Concomitant diseases that might be present at VS1 must be recorded in the eCRF.

Medical conditions that are diagnosed at VS1 will only be documented as adverse events, if they are known to have started or are suspected to have started after the ICF has been signed. All other medical findings at the medical examination at VS1 will be documented as medical history.

6.2.3. Prior and concomitant treatments and lifestyle

Any treatment that was given in addition to IMP during the trial is regarded as a concomitant treatment and must be documented on the appropriate pages of the eCRF, specifying drug taken, dose, route, start/stop date and reason for use.

Therapies administered within 3 months before VS1 will also be documented in the eCRF.

All concomitant drugs must be known to and approved by the investigator and should be maintained stable during the trial unless mandatory to increase or decrease the dose to ensure a better efficacy or a better safety for the subjects. All changes in therapy or in doses must be documented in the eCRF. The subject should mention all other drugs, including over the counter medication such as acetylsalicylic acid.

Consumption of alcohol will be recorded in the eCRF at VS1, consumption of grapefruit products and quinine-containing drinks not.

6.2.4. Modified Hoehn & Yahr stage

The investigator will assess the subject's Hoehn & Yahr stage as follows:

- 0 No signs of disease.
- 1 Unilateral disease.
- 1.5 Unilateral plus axial involvement.

- 2 Bilateral disease, without impairment of balance.
- 2.5 Mild bilateral disease, with recovery on pull test.
- 3 Mild to moderate bilateral disease; some postural instability; physically independent.
- 4 Severe disability; still able to walk or stand unassisted.
- 5 Wheelchair bound or bedridden unless aided.

6.2.5. Calculation of glomerular filtration rate

For the verification of exclusion criterion no. 9, the glomerular filtration rate will be calculated based on 2009 CKD-EPI creatinine equation [32] as follows:

$$\text{GFR [mL/min/1.73 m}^2\text{]} = 141 \times \min(\text{S}_{\text{Cr}}/\kappa, 1)^\alpha \times \max(\text{S}_{\text{Cr}}/\kappa, 1)^{-1.209} \times 0.993^{\text{Age}} \times 1.018 \text{ [if female]} \times 1.159 \text{ [if Black]}$$

S_{Cr} = standardised serum creatinine [mg/dL]

κ = 0.7 (females) or 0.9 (males)

α = -0.329 (females) or -0.411 (males)

$\min(\text{S}_{\text{Cr}}/\kappa, 1)$ = indicates the minimum of $\text{S}_{\text{Cr}}/\kappa$ or 1

$\max(\text{S}_{\text{Cr}}/\kappa, 1)$ = indicates the maximum of $\text{S}_{\text{Cr}}/\kappa$ or 1

age [years]

6.3. Safety Assessments

6.3.1. Adverse events

For adverse events see Section 7.

6.3.2. Safety laboratory and pregnancy tests

Serology, haematology, blood coagulation and biochemistry analyses will be performed by a central laboratory. Urinalysis (dipstick) and urine pregnancy test (women of childbearing potential only) will be performed by trial site staff on-site. For the list of parameters, see Section 14.2.

For safety laboratory tests, approximately 10 mL of blood will be collected at each blood withdrawal.

Laboratory values outside the normal ranges have to be assessed by the investigators if clinically significant abnormal or not clinically significant abnormal.

Each change to clinically significant abnormal laboratory value during the trial has to be documented as an AE in the eCRF unless the measurement is identified to be caused by a laboratory error and unless the underlying disease causing the change to laboratory abnormality is already documented. Clinically significant abnormal laboratory values at VS1 not related to any already documented underlying disease have to be documented as medical history.

6.3.3. Vital signs and weight

Vital signs (systolic and diastolic blood pressure as well as heart rate) will be measured twice: after 5 minutes supine rest and after 2 minutes in standing position (one set of supine and standing vital signs).

At VR, V1C and V2C three sets of supine and standing vital signs will be measured with 15-20 min intervals between the sets.

Weight will be measured in street clothes without shoes.

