6.1.1, 6.2.1	It has been clarified that height has to be measured at visit VS1.	--
6.1.3, 6.1.5, 6.3.6, 8.1.1, 8.3.2, 13	UPDRS part III was replaced by MDS-UPDRS. MDS-UPDRS will be completed at VR, V1B, V2B and V3B/EDV. Statistical methods (safety) and references were updated.	FDA
6.1.3	At visit VR, three measurements of orthostatic vital signs will be performed 15-20 min apart.	FDA
6.1.3, 6.1.5	QUIP-RS will be assessed.	FDA
6.1.6	The ± 1 time windows for visits V1C and V2C have been changed to -1/+7 time windows.	--
6.1.6	UPDRS Part III will not be completed at visits V1C and V2C. At visits V1C and V2C, three measurements of orthostatic vital signs will be performed 15-20 min apart.	FDA FDA
6.3.3	Orthostatic vital signs (supine and standing) will be measured instead of sitting vital signs.	FDA
6.3.7, 8.1.1, 13	The QUIP-RS questionnaire has been added.	FDA
8.3.1	Procedure in case of significant treatment by period interaction has been added.	--
8.3.2	Information on vital signs' analysis has been updated, QUIP-RS and MDS-UPDRS have been added.	FDA

Section(s)*	Change from Final Protocol Version 2.0, 08 March 2018, to Final Protocol Version 3.0, 27 April 2018	Change requested by
6.1.3, 6.1.5, 6.1.6, 6.3.5	C-SSRS will be performed at all on-site visits.	FDA (also requested by SÚKL)
4.3	Exclusion criterion no. 9 has been modified to exclude subjects with hepatic or renal impairment, regardless of severity.	FDA

Section(s)*	Change from Final Protocol Version 3.0, 27 April 2018 to Final Protocol Version 4.0, 30 May 2018	Change requested by
Title page	IND number has been added.	--
4.2, 7.3	Methods of contraception have been modified.	SÚKL
4.3	Multiple system atrophy (Shy-Drager syndrome) has been added to exclusion criterion no.2.	EC of the LÄK Thüringen
4.3	Exclusion criterion no. 3 has been modified to provide a more detailed description of cardiovascular disorders.	EC of the LÄK Thüringen, SÚKL and EC Sud-Ouest et Outre Mer III, France
4.3	Exclusion criteria no. 8 and 9 have been modified by deleting “significant abnormality in physical examination or clinical laboratory results at VS1” from criterion no. 9 and adding to criterion no.8.	--
4.3, 5.5	Exclusion criterion no. 11f and the section on prior and concomitant medication have been modified. Use of efficacious medication for Parkinson’s disease will be allowed if maintained at stable dosage levels.	SÚKL

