6.1. Description of Trial Visits

Seven on-site visits and five phone call visits are planned.

Due to the PVT and MoCA assessments on-site visits should always start in the morning.

Unscheduled (on-site or phone) visits at additional time points may be performed, if required. An administrative/logistic phone contact or on-site presence will not be documented as unscheduled visit in the eCRF.

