6.1.3. Visit VR

This randomisation/baseline visit is an on-site visit and will per definition take place on Day -1.

(Please note that there is no Day 0. The day after Day -1 is Day 1. Day 1 is the day of first IMP intake.)

The following procedures will be performed:

- Concomitant medication
- Check for eligibility
- Randomisation
- IMP dispensation
- Adverse event collection
- Safety laboratory (blood, urine)
- Pregnancy test (urine), for women of childbearing potential only
- Vital signs (3 sets of orthostatic vital signs 15-20 min apart)
- Weight
- 12-lead ECG (10 min supine)
- C-SSRS Since Last Visit version
- MDS-UPDRS
- QUIP-RS
- Physical examination
- ESS
- PVT at 10:00 h, 12:00 h, 14:00 h and 16:00 h (\pm 0:15 h each). If this PVT assessment schedule is too burdensome for the subject, it may be individually adapted to at least 3 assessments, with a time window of not less than 1 h between two PVT assessments. Once chosen, the timeframe should remain constant during the trial for each subject. Upload data
- MoCA
- Collect and charge actigraphy device
- Read out actigraphy device, upload data
- Issue actigraphy device (fully charged)
- Issue subject diary (treatment phase diary)
- Check subject diary (screening phase diary)
- Collect subject diary (screening phase diary)
- PK blood sample

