### 2.2 Trial Endpoints

#### 2.2.1 Safety Endpoints

The safety endpoints of this trial are

1. Adverse events
2. Safety laboratory
3. Vital signs change
4. Electrocardiogram assessments
5. Columbia-Suicide Severity Rating Scale (C-SSRS)

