### 5.5.3 Vital Signs

Vital signs (systolic and diastolic blood pressure as well as heart rate) will be measured twice: after 5 minutes supine rest and after 2 minutes in standing position (one set of supine and standing vital signs) at visits VS1, VR, V1B, V1C, V2B, V2C, and V3B/EDV.

At VR, V1C and V2C three sets of supine and standing vital signs will be measured with 15-20 min intervals between the sets.

Vital signs’ parameters will be summarised using the mean value at each visit. The mean will be calculated if there is at least one non-missing value for a given parameter.

Results for systolic blood pressure, diastolic blood pressure, and heart rate will be classified according to whether the value was lower than (L), within (N) or higher than (H) the reference range for that parameter. The normal ranges are provided in Table .

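### Supine and standing vital signs are paired at every on-site visit, but no planned table shows the within-subject postural change or how many subjects have a postural drop on each treatment

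*Protocol*

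**What the plan says.** Protocol 6.1 fixes the visit structure: "Seven on-site visits and five phone call visits are planned". SAP 5.5.3 places supine and standing measurement at all seven on-site visits: "one set of supine and standing vital signs) at visits VS1, VR, V1B, V1C, V2B, V2C, and V3B/EDV". Three of these visits carry repeats: "At VR, V1C and V2C three sets of supine and standing vital signs will be measured" (Protocol 6.3.3). The visit description for VR calls these sets orthostatic: "Vital signs (3 sets of orthostatic vital signs 15-20 min apart". The amendment log gives the origin of the paired design, with the FDA as requester: "Orthostatic vital signs (supine and standing) will be measured instead of sitting vital signs".

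The safety endpoint is worded only as "Vital signs change" (SAP 2.2.1). SAP 4.7 defines change as the value at a visit minus the baseline value, so it is a change between visits and not between positions.

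On analysis, SAP 5.5.3 says that the parameters "will be summarised using the mean value at each visit". Table 6 gives separate supine and standing ranges for systolic and diastolic pressure, and one range for heart rate with no position. Three tables follow: a summary with change from baseline (15.2.5.1.T), Low/Normal/High incidence (15.2.5.2.T) and a baseline-to-endpoint shift (15.2.5.3.T). Individual values go to Listing 16.2.8.1. Protocol 8.3.2 plans the same kinds of output.

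**The concern.** The reason for measuring a subject lying and then standing is the difference between the two. Neither Protocol 8.3.2, SAP 5.5.3, the output list in SAP 9.1 nor the list of changes in SAP section 7 mentions a standing-minus-supine variable, a category for a postural drop, or its incidence.

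Safety is the primary objective, and the subjects have Parkinson's disease and may be up to 80 years old. The documents show interest in postural response: Protocol 1.1 reports on orthostatic symptoms in phase I, and Protocol 5.5 makes freedom from orthostatic hypotension a condition for permitted antidepressants. At stake is whether the report can say, by treatment, how many subjects had a marked fall on standing and how variable that fall was.

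A second gap has the same cause. The visit-mean rule does not say that the mean is taken within position. Blood pressure is protected by its position-specific rows in Table 6. Heart rate is not, so supine and standing heart rate could be averaged together and the postural heart-rate response lost.

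**Working it through.** The plan states no figure for postural change, so there is nothing to reproduce. The check has three parts.

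**1. What is collected.** Three sets at each of VR, V1C and V2C, and one at each of VS1, V1B, V2B and V3B/EDV: 3 × 3 + 4 × 1 = 13 paired sets per completing subject.

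**2. What the abnormality tables can miss.** The inputs are the Table 6 limits, with the limits themselves counted as within range.
- Systolic: supine 90 to 140, standing 80 to 140. The largest fall that is Normal in both positions is 140 − 80 = 60 mmHg.
- Diastolic: 60 to 90 in both positions. The largest such fall is 90 − 60 = 30 mmHg.

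The incidence and shift tables show nothing for such a subject.

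**3. What the summary table leaves open.** Let supine and standing pressure each have SD s and within-subject correlation ρ. Then

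SD of change = s√(2(1 − ρ)), so ρ = 1 − (SD of change)² / (2s²).

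For a normally distributed fall with mean m,

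P(fall ≥ 20) = 1 − Φ((20 − m) / SD of change).

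All inputs here are assumed: s = 16 mmHg in both positions, m = 8 mmHg, and 20 mmHg as the event. Then 2s² = 512 and 20 − m = 12.

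| SD of change (mmHg) | Implied ρ | 12 / SD | P(fall ≥ 20) | Expected among 60 |
|---|---|---|---|---|
| 6 | 0.93 | 2.0 | 2.3% | 1.4 |
| 8 | 0.88 | 1.5 | 6.7% | 4.0 |
| 12 | 0.72 | 1.0 | 15.9% | 9.5 |
| 15 | 0.56 | 0.8 | 21.2% | 12.7 |

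All four rows have the same supine mean and SD and the same standing mean and SD. Only ρ differs, and no planned table reports it. The standard error of the mean fall is also undetermined: with 60 subjects it runs from 6/√60 = 0.77 to 15/√60 = 1.94 mmHg.

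The illustration depends on its assumptions. With mean falls of 5 to 12 mmHg, SDs of 14 to 18 mmHg in each position and correlations of 0.4 to 0.9, the share runs from 0.8% to 34.2%.

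**The case against.** The strongest reply is that the SAP faithfully carries out the protocol's vital-signs plan, that safety is descriptive, and that nothing is lost. Much of this stands.

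- A reader might infer that the planned outputs say nothing about postural change. They do say something. Subtracting the standing mean from the supine mean in Table 15.2.5.1.T approximates the mean fall, if both positions are shown and the same subjects contribute. Each subject's fall can be worked out from Listing 16.2.8.1, and symptomatic episodes can be reported as adverse events. What is missing is the SD of the fall and the count of subjects, and counting from a listing after unblinding is not a pre-specified analysis.
- A reader might infer that phase I pointed to falls in pressure. Protocol 1.1 and 1.4.1 report increases in blood pressure and heart rate, at 400 mg/50 mg, and no orthostatic symptoms on any treatment. That was in nine healthy men, so it does not settle the question in this population, but it is no evidence of a fall either.
- A reader might infer that the planned tables would look alike whatever the spread of the fall. That holds only with both position SDs fixed. If the supine SD were 16 mmHg and the change independent of it, the standing SD would go from √(256 + 36) = 17.1 to √(256 + 225) = 21.9 mmHg, a visible difference.
- No orthostatic objective is written. The interest is inferred from the choice of measurement and the endpoint.
- The table shells are separate attachments and were not available. They may show more than the SAP text does.
- Because VR has three sets and the end-of-treatment visits one, it may be tempting to use only the first set at VR, V1C and V2C. That discards two of three sets and departs from the planned visit mean. The end-of-treatment comparison between treatments is single set against single set in any case.

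**Conclusion.** The point holds in a limited form: the incidence and variability of postural drops by treatment cannot be read from the tables in the SAP text. Falls of up to 60 mmHg systolic or 30 mmHg diastolic can be Normal in both positions; that follows from Table 6 alone. The range of about 2% to 21% of subjects falling 20 mmHg or more is an illustration. It rests on assumed SDs of 16 mmHg fixed in both positions, an assumed mean fall of 8 mmHg and normality. The handling of heart rate is ambiguous as written; the text does not show that pooling is intended.

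This is not a contradiction between protocol and SAP. It does not affect the sample size or the efficacy analysis, and the data are kept. It is a cheap improvement that lets the primary safety objective use measurements already taken.

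**What to change.** In SAP 5.5.3:

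- Derive standing minus supine systolic pressure, diastolic pressure and heart rate within each set, and average the sets within a visit, in line with the existing visit-mean rule. Working within the set keeps the pairing when one reading is missing.
- Summarise the postural change, and its change from baseline, by treatment and visit.
- Tabulate by treatment the number of subjects meeting a postural-drop category fixed before unblinding. A fall of 20 mmHg systolic or 10 mmHg diastolic is one example. These cut-offs are an assumption, appear in neither document, and serve only as a reporting category.
- State that visit means are taken within position, including for heart rate, and give the position to which the heart-rate range in Table 6 applies.

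The cost is three derived variables, one event flag and two tables, with no new measurements.

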6.3.4. Electrocardiogram (ECG)

The sponsor will provide the investigator with the ECG device that shall be used in this trial. Twelve-lead ECG will be recorded after 10 minutes in supine position. ECG reading will be performed centrally by the provider specified in Section 14.1 and will include

- ECG measured parameters as intervals (PR, QRS, QT)
- Pattern of change for PR, QRS and QT versus ECG from baseline
- Derived ECG parameters (QTcF, heart rate)

ECG will be recorded at VS1, VR, V1B, V1C, V2B, V2C and V3B.

6.3.5. Columbia-Suicide Severity Rating Scale (C-SSRS)

The C-SSRS is a tool that was developed to facilitate a prospective, systematic monitoring for the emergence of suicidal tendencies in clinical studies. It is used to compare the occurrence, severity, and frequency of suicide-related thoughts and behaviours during treatment in a clinical trial.

The C-SSRS Screening version will be used at VS1 to obtain baseline data. The recall period will be set to 12 months / 1 year. Exclusion criterion no.6 will be met if the subject answers “yes” to items 4 and/or 5 of the C-SSRS only referring to the last month before VS1.

The C-SSRS Since Last Visit version will be used to capture changes in the subject’s status at VR, V1B, V1C, V2B, V2C and V3B.

Subjects who answer “yes” to point 4 and/or 5 of the C-SSRS will be withdrawn from the trial and will be sent for psychiatric consultation.

6.3.6. Movement Disorder Society-Sponsored Version of Unified Parkinson's Disease Rating Scale (MDS-UPDRS)

The MDS-UPDRS is a comprehensive assessment of both motor and non-motor symptoms associated with Parkinson's disease. [33] It has four parts:

- Part I (non-motor experiences of daily living, 13 items), further divided into:
 - Part IA focuses on complex behaviors and is completed by the investigator, based on interview with the subject
 - Part IB focuses on non-motor experiences of daily living and is completed by the subject
- Part II (motor experiences of daily living, 13 items), completed by the subject
- Part III (motor examination, 33 items), completed by the investigator
- Part IV (motor complications, 6 items) completed by the investigator, based on interview with the subject.

The MDS-UPDRS rates 65 items on a 5-point scale: normal (0), slight (1), mild (2), moderate (3) and severe (4).

The MDS-UPDRS will be completed at baseline and at the end of each treatment period, i.e. at visits: VR, V1B, V2B and V3B.

6.3.7. Questionnaire for Impulsive-Compulsive Disorders in Parkinson's Disease – Rating Scale (QUIP-RS)

The QUIP-RS is a validated tool designed to measure the severity of symptoms of impulse control disorders (ICDs) and related disorders. [34] The QUIP-RS consists of four primary questions, each applied to four ICDs (compulsive gambling, buying, eating and sexual behaviour) and three related disorders (medication use, punting and hobbyism). The QUIP-RS uses a 5-point Likert scale (score 0-4 for each question) to rate the severity of each symptom based on its weekly frequency. To be applicable in this trial, the standard 4-week recall period will be reduced to one week.

The total ICD score ranges from 0 to 64, and the total QUIP-RS score for all ICDs and related disorders ranges from 0 to 112.

The QUIP-RS will be provided in a local language. The investigator will complete the scales based on interview with the subject.

The QUIP-RS will be completed at baseline and at the end of each treatment period (visits: VR, V1B, V2B and V3B).

6.3.8. Physical examination

Physical examination includes an examination of the organ systems head, neck, eyes, ear-nose-throat, heart, respiratory, gastrointestinal, hepatic, urogenital, musculoskeletal, vascular, lymphatic, dermatologic, central-nervous system (CNS) and psychiatric.

6.4. Efficacy Assessments

6.4.1. Epworth Sleepiness Scale (ESS)

The subject will complete the Epworth Sleepiness Scale (ESS, 1-week recall period). The questionnaire will be provided in local language. Site staff will enter ESS data into the eCRF.

6.4.2. Psychomotor Vigilance Test (PVT)

The psychomotor vigilance test is an objective tool used to measure the subject's behavioural alertness. [35] It is a visual test which involves measuring

- Mean response time (ms)
- Number of lapses
- Number of total errors

The PVT requires no training, only a brief explanation of the procedure to the subject prior to the start of the test. It will be performed in the 'on' state.

PVT will be performed at 10:00 h, 12:00 h, 14:00 h and 16:00 h (\pm 0:15 h each). If this PVT assessment schedule is too burdensome for the subject, it may be individually adapted to at least 3 assessments, with a time window of not less than 1 h between two PVT assessments. Once chosen, the timeframe of PVT assessments should remain constant during the trial for each subject.

The sponsor will provide the investigator with a PVT-192 device to perform a 3-minutes PVT and a notebook computer to read out data.

6.4.3. Montreal Cognitive Assessment (MoCA)

The MoCA is a brief screening instrument to detect mild cognitive impairment. It is a paper-and-pencil tool that requires approximately 10 minutes and will be administered by the investigator. It will be

performed in the 'on' state. The MoCA assesses multiple cognitive domains including attention, concentration, executive functions, memory, language, visuospatial skills, abstraction, calculation and orientation. One part of the paper questionnaire will be completed by the subject, another part will be completed by the investigator. Site staff will enter MoCA data into the eCRF.

The MoCA questionnaire will be provided in local language. To decrease possible learning effects, the three (equivalent) versions 7.1, 7.2 and 7.3 will be used in alternation.

MoCA should be performed in the morning.

MoCA scores range between 0 and 30. A score of 26 or over is considered to be normal.

